6. STUDY PROCEDURES

Study visits

Visits	Procedures
Visit 1 – before surgery	
- Obtain informed consent- ADL questionnaire (see next section)- Visual analog scale for pain (VAS): pain on a scale of 1 to 10 
The measurements are part of standard care and performed by caregivers
 
- Perform the following measurements: range of motion of the PIP joint of the affected finger (including noting any flexion contracture), distance fingertip to distal palmar crease (DPC), and grip strength using Jamar 2 setting.
Visit/Telephone call 2 (2-4 days after surgery)	
- Take the following questionnaire:
1. Are you able to return to activities of daily living, and what activities do you still have trouble doing? You can list the activities you are having trouble with.2. VAS3. How many oxycodone or other narcotic medications are you taking post-op4. Are you able to return to work?

	
5. Are you satisfied with the procedure, and would you choose to have it again for a similar problem?
 
- Take the ADL questionnaire (see next section)- If in person (part of standard care, only collected by study staff, measurements performed by caregivers): Perform the following measurements: range of motion of the PIP joint of the affected finger (including noting any flexion contracture), distance fingertip to distal palmar crease (DPC), and grip strength using Jamar 2 setting.
Visit/Telephone call 3 (6-8 days after surgery)	
- Take the following questionnaire:
1. Are you able to return to activities of daily living, and what activities do you still have trouble doing? You can list the activities you are having trouble with.2. VAS3. How many oxycodone or other narcotic medications are you taking post-op4. Are you able to return to work?5. Are you satisfied with the procedure, and would you choose to have it again for a similar problem?- Take the ADL questionnaire (see next section)- If in person (part of standard care, only collected by study staff, measurements performed by caregivers): Perform the following measurements: range of motion of the PIP joint of the affected finger (including noting any flexion contracture), distance fingertip to distal palmar crease (DPC), and grip strength using Jamar 2 setting.

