	
2. VAS3. How many oxycodone or other narcotic medications are you taking post-op4. Are you able to return to work?5. Are you satisfied with the procedure, and would you choose to have it again for a similar problem? 
- Take the ADL questionnaire (see next section)- If in person (part of standard care, only collected by study staff, measurements performed by caregivers): Perform the following measurements: range of motion of the PIP joint of the affected finger (including noting any flexion contracture), distance fingertip to distal palmar crease (DPC), and grip strength using Jamar 2 setting.-
Visit/Telephone call 7 (6 months +- 1 week after surgery)	
- Take the following questionnaire:- 1. Are you able to return to activities of daily living, and what activities do you still have trouble doing? You can list the activities you are having trouble with.2. VAS3. How many oxycodone or other narcotic medications are you taking post-op4. Are you able to return to work?5. Are you satisfied with the procedure, and would you choose to have it again for a similar problem? 
- Take the ADL questionnaire (see next section)- If in person (part of standard care, only collected by study staff, measurements performed by caregivers): Perform the following measurements: range of motion of the PIP joint of the affected finger (including noting any flexion contracture), distance fingertip to distal palmar crease (DPC), and grip strength using Jamar 2 setting.

We will call or e-mail patients to ask them to complete questionnaires (see above) through Redcap.

Procedures

The intervention groups consist of:

- Open trigger finger release
 - o The A1 pulley is reached through a transverse incision under local anesthesia and monitored anesthesia care. It is then divided longitudinally. The patient is asked to flex and extend the affected finger. If triggering has been resolved, the wound is closed with sutures (12).
- Ultrasound-guided trigger finger release
 - o The A1 pulley is identified with the use of ultrasound. The pulley is released with a trigger finger device under local anesthesia and monitored anesthesia care (9).

Specific data variables to be collected

The variables that will be collected are:

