- Range of motion of the PIP joint of the affected finger using a goniometer (in degrees), including any flexion contracture + Distance of fingertip from DPC
- Grip strength in the affected as well as contralateral hand using a dynamometer at Jamar 3 setting (in lbs)
- Return to activities of daily living. One question is: 'What activities can't you do?'. We also take a questionnaire to rate their ability to do certain activities (see questionnaire under this section). Patients can rate their ability to perform each activity on a scale from 1 to 5 (1 indicating no difficulty and 5 indicating unable to perform).
- VAS (a pain scale from 1 – 10, reported by the patient)
- How many oxycodone or other narcotic medications are you taking post-op? The number of pills taken will be given.
- Return to work. Patients give a date of when they started working again. Then we'll calculate the return to work in weeks
- Are you satisfied with the procedure, and would you choose to have it again for a similar problem? Answered with yes or no.
- Complications (i.e., trigger finger recurrence, infection, bleeding, etc.)

ADL questionnaire

Mass General Brigham Institutional Review Board
Intervention/Interaction Detailed Protocol

Opening jar	1	2	3	4	5
Driving	1	2	3	4	5
Household Chores	1	2	3	4	5
Carrying Groceries	1	2	3	4	5
Buttoning	1	2	3	4	5
Bathing	1	2	3	4	5
Cooking	1	2	3	4	5
Writing	1	2	3	4	5
Dressing	1	2	3	4	5
Shopping	1	2	3	4	5
Holding a book	1	2	3	4	5
Eating	1	2	3	4	5
Using a Computer	1	2	3	4	5
Holding a Phone	1	2	3	4	5
Using Toilet	1	2	3	4	5

Description of plans for return of research results as applicable

Not applicable

Definition of primary and secondary outcomes/endpoints

Primary endpoints:

- The 5 questions asked in the section above, together with the *ADL questionnaire*
- Recurrence of trigger finger or incomplete release

Secondary endpoints:

- Range of motion of the PIP joint of the affected finger (including noting any flexion contracture)
- Distance fingertip to distal palmar crease
- Grip strength in the affected hand
- Other complications than recurrence of trigger finger or incomplete release

Local site restrictions or site-specific procedures as applicable

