The visits during the first 3 months are part of standard care. Patients with persistent problems will be seen at the 6-month follow-up as part of standard care. If they are doing well clinically, we will only contact them by phone or email to complete these questionnaires using Redcap (see above for the scheme).

Remuneration as applicable

There is no remuneration for this study.

2. Risks and Discomforts

Trigger finger release is a standard procedure (whether it is open or ultrasound-guided) for a trigger finger.

This study's foreseeable risks and discomforts include the time required to complete the measurements and questionnaires. All electronic information (like measurements in Excel files) will be stored on

password-protected computers in a locked office that only study staff members can access. Study data of the questionnaires will be collected and maintained electronically using REDCap, a secure and HIPAA-compliant web-based application to which only study staff will have access. This limits the risk of a data and confidentiality breach, though it is a possibility.

We do not foresee additional risks for subjects participating in the study. Subjects will receive usual care, regardless of their participation. Physicians will be readily accessible for consultation should a subject experience discomfort while completing the measurements and questionnaires or at any time during the study.

3. Benefits

Patients will not receive any direct benefits from this study. However, their participation will help us to determine clinical outcomes after ultrasound-guided and open trigger finger release, which can help patients and physicians in shared decision-making. Potential benefits of ultrasound-guided trigger finger release could be a faster recovery (faster return to work) and better patient-reported aesthetics.

4. Statistical Analysis

Normally distributed continuous data will be stated as mean \pm standard deviations, non-normally distributed continuous data as medians with interquartile ranges and categorical data as frequencies and percentages.

We plan to statistically compare the postoperative clinical data of open trigger finger release to ultrasound-guided trigger finger release.

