We will use a student t-test to analyze normally distributed continuous data. When we compare data at two different time points within a group, we will use a paired student t-test. When we compare continuous data of two different groups, we will use an unpaired student t-test.

We will use a Mann-Whitney U test if the continuous data is not normally distributed.

We will use Fischer's exact test or a Chi-squared test for differences in categorical variables, depending on the number of events in the different groups.

Power analysis

We have performed a power analysis to find differences between two independent means (normally distributed) with alpha = 0.05, power = 0.80, and effect size 0.5. This would require a total sample size of 102 patients (51 in each group). If the data is non-normally distributed with the same alpha, power, and effect size, we would need a total of 106 patients (53 in each group).

This power analysis is performed for our most important primary outcomes: the 5-question and ADL questionnaires.

5. Monitoring and Quality Assurance

The full-time research coordinator and principal investigator are responsible for adherence to all IRB policies and guidelines and for the accuracy and completeness of all forms, entries, and informed consent.

Study data will be maintained in a locked filing cabinet and/or on password-protected computers. Questionnaires and self-reported responses will not become part of the subject's medical record. Hard copies of study-related data and forms will be stored in a lockable file cabinet. Only the investigators and study staff will have access to this information. Any magnetic or electronic information will be saved in password-protected computers, which only study staff members can access. REDCap, secure and HIPAA-compliant, will be used to collect all answers.

For guidance, refer to the following Partners policies:

Data and Safety Monitoring Plans and Quality Assurance

https://partnershealthcare-public.sharepoint.com/ClinicalResearch/DSMP_in_Human_Subjects_Research.pdf

Reporting Unanticipated Problems (including Adverse Events)

https://partnershealthcare-public.sharepoint.com/ClinicalResearch/Reporting_Unanticipated_Problems_including_Adverse_Events.pdf

6. Privacy and Confidentiality

- Study procedures will be conducted in a private setting
- Only data and/or specimens necessary for the conduct of the study will be collected

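### Five questions, an unscored ADL form and recurrence are all primary over six contacts, with no chosen endpoint or error control, and one 80% power figure is claimed for both questionnaires

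*Combined protocol and SAP*

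**What the plan says.** Under the heading on primary and secondary outcomes in Study Procedures, there are two primary entries. The first is "The 5 questions asked in the section above, together with the" ADL questionnaire. The second is "Recurrence of trigger finger or incomplete release". The five questions cover return to daily activities, VAS pain, narcotic count, return to work and satisfaction. The ADL form has 15 activities, each rated 1 to 5, and no total or mean is defined.

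The visit table repeats the questions and the form at six postoperative contacts, from "Visit/Telephone call 2 (2-4 days after surgery") to "Visit/Telephone call 7 (6 months +- 1 week after surgery"). Return to work is also described as one value per patient: "Patients give a date of when they started working again", converted to weeks.

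The Statistical Analysis section states the aim in one sentence: "We plan to statistically compare the postoperative clinical data of open trigger finger release to ultrasound-guided trigger finger release". Tests then follow data type: t-test or Mann-Whitney for continuous data, and for the rest Fisher's "exact test or a Chi-squared test for differences in categorical variables, depending on the number of events in the different groups".

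The power paragraph uses alpha 0.05, power 0.80 and effect size 0.5 for two independent means. It arrives at 102 patients (51 per group), or 106 (53 per group) if the data are not normal. It applies this to the 5-question and ADL questionnaires, which it ranks as the leading primary outcomes. Sidedness is not stated.

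**The concern.** A primary endpoint fixes in advance which result answers the question. Here any of several items at any of six contacts could be presented as the primary finding. A mixed outcome, such as less pain in the first week and no difference at six months, has no agreed reading. The Benefits section says ultrasound guidance "could be a faster recovery (faster return to work"), but the endpoint list does not rank return to work above the other items.

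Two things are at stake. One is the false-positive rate across the primary set if the items and contacts are each tested at 0.05. The other is what the 80% power refers to, since a calculation for one difference in means is attached to two whole questionnaires, one mixing numeric and yes/no answers and the other without a score.

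**Working it through.** **1. The plan's own sample size.** Inputs from the power paragraph: alpha 0.05, power 0.80, d = 0.5, equal groups. The normal approximation is n per group = 2(z_alpha + z_power)²/d².

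- One-sided: 2(1.645 + 0.842)²/0.25 = 49.5. The exact t-test gives 50.15, so 51 per group, **102** in all. Mann-Whitney (efficiency 3/π = 0.955): 50.15/0.955 = 52.5, so 53 per group, **106** in all. Both stated figures are matched.
- Two-sided: 2(1.960 + 0.842)²/0.25 = 62.8. The exact t-test gives 63.8, so 64 per group, 128 in all. Mann-Whitney: 66.8, so 67 per group, 134 in all. Neither stated figure is matched.

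| Test | n per group | One-sided power | Two-sided power | d detectable at 80%, two-sided |
|---|---|---|---|---|
| t-test | 51 | 80.6% | 70.6% | 0.560 |
| Mann-Whitney | 53 | 80.3% | 70.2% | 0.562 |

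**2. Number of primary comparisons left open.** Return to ADL, VAS, narcotic count, satisfaction and one ADL score, at 6 contacts each: 5 × 6 = 30. Add return to work in weeks (1) and recurrence or incomplete release (1): **32**, of which 19 are numeric and 13 yes/no. If return to work is compared at every contact, the count is 6 × 6 + 1 = 37. If the ADL items are tested singly, with return to work counted once, it is (15 + 4) × 6 + 2 = 116.

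**3. Chance of at least one false positive if all 32 are tested at 0.05.** Under independence it is 1 − 0.95³² = 0.81, an upper limit because answers from the same patient are correlated. The documents give no correlations, so a range is assumed. The model draws 32 normal test statistics 200,000 times. Their correlation is an outcome value when outcomes differ, multiplied by a visit value when visits differ. Each once-only variable correlates with the repeated ones at outcome value × √(visit value).

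| Assumed outcome/visit correlation | Chance of ≥ 1 false positive, two-sided |
|---|---|
| 0.3/0.3 | 0.74 |
| 0.5/0.7 | 0.52 |
| 0.7/0.8 | 0.37 to 0.38 |
| 0.9/0.9 | 0.21 |

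Fisher's test is conservative: with 51 per group its true size is 0.0245 at an assumed yes-rate of 85% and 0.0075 at 95%. Using those sizes for the yes/no items, the first row becomes 0.59–0.66 and the last 0.18. Because sidedness is unstated, a simpler model with one common correlation of 0.3, 0.5, 0.7 or 0.9 was also run: 0.68, 0.52, 0.35 and 0.17 two-sided, and 0.54, 0.41, 0.28 and 0.15 one-sided. Every figure is at least three times 0.05.

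**4. What the power figure can describe.** A difference-in-means calculation could serve VAS, narcotic count, return to work in weeks, or an ADL score once defined, each as one comparison (for the repeated measures, at one contact). It does not describe the yes/no items.

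**5. Power with adjustment for the preoperative score.** With baseline correlation r and a baseline difference between groups of Δ SD, the effective d is 0.5/√[(1 − r²)(1 + Δ²/4)]. Both r and Δ are assumed. The table is for 51 per group, two-sided.

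| r | Δ = 0: effective d, power | Δ = 0.5: effective d, power |
|---|---|---|
| 0.3 | 0.524, 75% | 0.509, 72% |
| 0.4 | 0.546, 78% | 0.529, 75% |
| 0.5 | 0.577, 82% | 0.560, 80% |

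**The case against.** The strongest reply is that this is a non-randomised cohort added to usual care, in which one surgeon performs every ultrasound-guided release. Confounding threatens the inference more than multiplicity does, and the plan never commits to running every test. That is fair as to priority, and it is why the count is of comparisons left open. It does not remove the defect, because the plan does propose a statistical comparison, sets an alpha and claims a power.

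It can also be said that the plan has a ranking, since the power paragraph places the questionnaires above recurrence. That stands, so it would be wrong to say that nothing is ranked. The ranking still selects no question, score or contact.

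The false-positive figures depend wholly on assumed correlations and yes-rates. They are illustrations, and 0.81 must not be read as an estimate.

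Two further inferences are tempting and unsupported:

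- For satisfaction at an assumed 85% against 95%, with 51 per group, two-sided power is 25% (Fisher) to 39% (uncorrected chi-squared). A reader might set this against the claimed 80% as the penalty for a yes/no item. The two are not comparable. That difference is an effect of h = 0.34, smaller than 0.5, and a two-sided t-test at that effect has only about 41%. At h = 0.5, one-sided, uncorrected chi-squared gives 82% and Fisher 66%, so a penalty arises mainly under Fisher.
- A reader might suppose that baseline adjustment restores 80% with 102 patients, since r = 0.45 does so when groups are balanced. Treatment follows the surgeon, so balance is not assured. At an assumed 0.5 SD imbalance the same r gives about 77.5%.

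**Conclusion.** The concern holds. The primary set leaves about 32 comparisons open, assuming one ADL score per contact and return to work counted once, with no selection among them and no error control. If all were tested at a two-sided 0.05, the illustrative chance of at least one false-positive primary result is about 0.2 to 0.7, depending on assumed correlations.

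The power calculation is arithmetically sound for one difference in means at effect size 0.5, tested one-sided at 5%. It cannot be claimed for both questionnaires as a block. For the ADL form the obstacle is the missing score; for the yes/no items it is the type of calculation. If the intended test is two-sided, power for even one such comparison is about 71% (t-test, 51 per group) or 70% (Mann-Whitney, 53 per group). Since sidedness is unstated, the documents do not show that the team meant a two-sided test and miscalculated; they show only that the stated numbers fit a one-sided one.

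**What to change.** Before data are examined, name one primary endpoint at one contact of the team's choosing. One example is the mean of answered ADL items, with a stated rule for unanswered items, compared between groups with adjustment for the preoperative score. That score should be available, because Subject Enrollment withdraws anyone who has not completed the preoperative questionnaire. Alternatively, name a small set of co-primaries with alpha split between them, which could retain recurrence. Two co-primary means at 0.025 each, d = 0.5 and 80% power per test, need 64 per group one-sided or 78 two-sided.

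Make the remaining questions and contacts secondary, reported with confidence intervals. Restrict the power statement to the chosen endpoint, state whether the test is one- or two-sided, and restate the power. For a single two-sided test the options are to report about 70–71% (detectable d about 0.56 at 80%) or to recruit 128 (t-test) or 134 (Mann-Whitney) in all. Any gain claimed from baseline adjustment should state the assumed correlation and the assumption about baseline balance.

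The cost is protocol wording. Other items and contacts can no longer be called primary, and the stated power may fall. None of this addresses confounding by surgeon or by treatment choice.

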3. General Description of Study Design

Retrospective part

Patient characteristics and disease-related (trigger finger) variables will be collected retrospectively from patient charts on EPIC.

Prospective part

This will be a prospective two-arm study. Patients will either be treated with ultrasound-guided trigger finger release or open trigger finger release (conventional method). [name] is the only surgeon within the Mass General Brigham (MGB) hospitals that performs ultrasound-guided trigger finger release. All other surgeons perform open trigger finger releases.

Surgeons will measure range of motion and grip strength preoperatively and during postoperative visits, which is part of routine care. We will also administer questionnaires to see how patients are doing postoperatively. See the '6. Study Procedures' for a more elaborate description of the visits.

4. Subject Selection

Inclusion criteria:

1. ≥ 18 years of age
2. Clinical diagnosis of trigger finger
3. Patient has failed conservative treatment or elects not to undergo conservative treatment
4. Surgeon agrees that surgery is indicated
5. Subject agrees to complete follow-up questionnaires over a 6-month period

Exclusion criteria:

1. Prior surgery on the target finger
2. History of prior surgical pulley release in the target hand
3. History of prior surgical pulley release in the contralateral hand within 3 months of enrollment or with persistent symptoms that interfere with normal daily activities or work at the time of consent
4. Corticosteroid injection in the target finger or hand within 6 weeks of surgery
5. Presence of additional process in the target wrist or hand requiring additional intervention beyond pulley release (e.g., neurolysis, mass removal, tenosynovectomy)
6. Clinically significant trauma or deformity of the upper limb (shoulder to hand) on the target side
7. Clinically significant vascular disease (including Raynaud's phenomenon) of the upper limb (shoulder to hand) on the target side
8. Clinically significant neurological disorder (including complex regional pain syndrome) of the upper limb (shoulder to hand) on the target side
9. Planned surgical or interventional procedure on the contralateral wrist or hand

10. Systemic inflammatory disease (e.g., rheumatoid arthritis, lupus)
11. Amyloidosis
12. Diabetes not controlled by a stable dose of medication over the past three months
13. Pregnant or planning pregnancy in the next 6 months
14. Workers' compensation subjects

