Telephone Script – Clinical and Patient-Reported Outcomes After Ultrasound-guided vs Open Trigger Finger Release

"Hello, is this Mr./Mrs. X? My name is [name]. I am a researcher from the Hand and Upper Extremity Service at [Massachusetts General Hospital/Brigham and Women's Hospital]. I am following up with you about the study you are enrolled in titled, "Clinical and Patient-Reported Outcomes After Ultrasound-guided vs Open Trigger Finger Release" to see if you would be able to take our questionnaire. Would now be an OK time to speak about this?"

If no: "Is there a better time to speak in the future?"

If yes:

"I will first revise what the study is about that you are enrolled in. We are studying the clinical and patient-reported outcomes of patients who had ultrasound-guided or open surgery for a trigger finger. Basically, we would be interested in hearing about your symptoms, hand functionality, and return to work since the operation. The entire process should take less than 5 minutes of your time and would be very valuable to us as clinicians and surgeons in the care of patients like you. Would you be interested in filling out the questionnaire over the phone or through e-mail?"

Alternatively, we would be happy to mail you the forms to complete with a self-addressed stamped envelope for return."

If yes:

Proceed with details of RedCap personalized sign-on or alternatively mailing of forms.

If no:

"We thank you for your time. Please do not hesitate to call if you would be willing to help in the future."

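### Recurrence is a primary endpoint that no question asks about; 6-month hand measurements are by rule confined to patients with persistent problems; and the grip setting contradicts itself

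*Combined protocol and SAP*

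**What the plan says.** **Recurrence.** Section 6 (Definition of primary and secondary outcomes/endpoints) lists two primary endpoints: the five questions with the ADL questionnaire, and "Recurrence of trigger finger or incomplete release". As collected data, recurrence otherwise appears only as an example in the variable list: "Complications (i.e., trigger finger recurrence, infection, bleeding, etc". No row of the Study visits table mentions recurrence or complications. Three other places bear on capture:

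- Section 3, Retrospective part: "Patient characteristics and disease-related (trigger finger) variables will be collected retrospectively from patient charts on EPIC". Postoperative recurrence is not mentioned.
- Section 5, Monitoring and Quality Assurance: "Questionnaires and self-reported responses will not become part of the subject's medical record".
- Telephone Script: "we would be interested in hearing about your symptoms, hand functionality, and return to work since the operation". No form item records triggering.

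**Six-month measurements.** From Visit 2 to Visit 7, motion of the PIP joint, fingertip-to-crease distance and grip carry the condition "If in person (part of standard care, only collected by study staff, measurements performed by caregivers". Section 6 (Local site restrictions) states who comes in at 6 months: "Patients with persistent problems will be seen at the 6-month follow-up as part of standard care". For the rest: "If they are doing well clinically, we will only contact them by phone or email to complete these questionnaires using Redcap". Section 4, Statistical Analysis, plans between-arm comparisons of the postoperative clinical data and excludes no time point.

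**Grip.** All seven visit rows specify Jamar 2. The variable list specifies Jamar 3.

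**The concern.** A primary endpoint needs a way of being observed that is the same for every patient in both arms. Here it depends on whether a patient returns to clinic, on what the surgeon writes in the chart, and on what a patient volunteers. Section 3 says that one surgeon performs all the ultrasound-guided releases and the other surgeons perform the open ones. Unstructured detection may therefore differ by arm. If events are few, one missed case can decide the result.

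The 6-month rule selects patients for measurement on their outcome. Any test of motion, crease distance or grip at that visit would compare the problem cases of one arm with those of the other, not the two arms. The threshold for being seen may also differ between surgeons.

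If both grip settings were used, the values could not be pooled cleanly across visits or arms.

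**Working it through.** **1. Is there any item on triggering?** The five questions cover activities, pain, narcotic use, work and satisfaction. The 15 ADL items are tasks, from opening a jar to using the toilet. None asks about catching, locking or retreatment. Question 1 allows free text, but about activities. The plan gives no criterion, assessor or time point, and nothing separates incomplete release from later recurrence.

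**2. What one missed recurrence does.** The input is 51 per arm (Power analysis). That figure reproduces only as a one-sided t-test: 50.15, rounded up to 51. The documents give no recurrence rate, so the counts below are examples.

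- One case: 1/51 = 1.96 percentage points.
- Fisher's exact test, two-sided, 51 per arm:

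| Recurrences | p |
|---|---|
| 6 vs 0 | 0.027 |
| 5 vs 0 | 0.056 |
| 4 vs 0 | 0.12 |
| 3 vs 0 | 0.24 |

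**3. Selection at 6 months.** The documents give neither the shares seen nor the link between symptoms and the measurements. Assumptions for illustration:

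- The measure and a symptom score are bivariate normal with SD 1, higher is better, and their correlation is r = 0.3 to 0.8.
- The true difference in the measure is d (ultrasound minus open).
- A patient is seen if the symptom score falls below a cutoff.

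In each arm let c = Φ⁻¹(share seen) and λ(c) = −φ(c)/Φ(c). The mean among those seen is the arm mean plus r·λ(c), so

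difference among those seen = d + r·[λ(c_us) − λ(c_open)].

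*(A) One cutoff shared by both arms, d = 0.5.* Let ultrasound patients have symptom scores better by s, so c_us = c_open − s.

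- Open share 10%, s = 0.5: c_open = −1.282, λ = −1.755; c_us = −1.782, λ = −2.181. The result is 0.5 + 0.3 × (−0.426) = 0.372, or 0.5 + 0.8 × (−0.426) = 0.159.
- Open share 30%, s = 0.5: λ = −1.159 and −1.545, giving 0.384 (r = 0.3) or 0.191 (r = 0.8).
- If symptoms differ only through the measure (s = 0.5r): 0.462 and 0.228 at 10%; 0.466 and 0.255 at 30%.

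The range is 0.16 to 0.47 SD.

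*(B) Cutoffs that differ by arm, d = 0.5.*

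| Open seen | Ultrasound seen | r = 0.3 | r = 0.8 |
|---|---|---|---|
| 10% | 30% | 0.679 | 0.977 |
| 30% | 10% | 0.321 | 0.023 |
| 15% | 15% | 0.500 | 0.500 |

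*(C) No true difference in the measure (d = 0), symptoms differ by s = 0.5, shared cutoff.* The false difference is −0.128 (r = 0.3) to −0.341 (r = 0.8) at 10% open seen, and −0.116 to −0.309 at 30%. It favors open release.

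**4. Grip.** Jamar 2 in seven visit rows and Jamar 3 in the variable list cannot both be the study's setting. The documents do not give the size of any shift between settings.

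**The case against.** **Recurrence would mostly be found.** It is on the list of variables to collect, charts are a named source, visits in the first 3 months are standard care, and a patient whose finger still triggers is plausibly not doing well and would be seen at 6 months. This stands in part and narrows the gap to mild, resolved or elsewhere-treated recurrence in remotely followed patients. It does not supply a definition or make detection equal between arms. Every postoperative row is headed as a visit or a telephone call, so even early contacts may be remote.

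**Questionnaire remarks are not lost.** Answers kept out of the chart are still in REDCap, where study staff can read them. That is right: the chart rule only means that chart review would not find such a remark. The point that remains is that no item prompts it.

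**The Fisher example sits on the 0.05 line.** True. At 4 or fewer vs 0, losing a case does not change significance. The example shows what can happen, not what is expected.

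**No 6-month test of these measures is specified, and they are secondary and unpowered.** Both statements are correct, but the general comparison covers all postoperative clinical data, so the plan as written permits the test.

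**The selection figures rest on assumptions, and sparse data may matter more.** Fair. With a shared cutoff, s = 0.5 and 10% of open patients seen, the ultrasound share is 3.7%, or about 5 vs 2 patients of 51. The standard error is √(1/5 + 1/2) = 0.84 SD, larger than the bias shown for that case. This is a further reason not to run the test.

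**Conclusion.** All three parts hold.

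- The main one is recurrence: a primary endpoint has no item, definition, source or schedule, and some cases in remotely followed patients have no stated route to capture. The share missed cannot be estimated from the documents. Each missed case costs 2.0 percentage points at 51 per arm.
- The 6-month motion, crease-distance and grip values come from an outcome-selected subset. A between-arm test would be biased by an unknown amount in an unknown direction. The illustrated results for a true 0.5 SD run from 0.02 to 0.98 SD, including no bias when equal shares are seen. They depend on the assumed normality, correlation, shares seen and true difference. The powered questionnaires are sent to everyone and do not share this defect.
- The grip settings contradict each other. Nothing shows that settings were mixed in practice.

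The textual gaps are certain; the size of their effect is not. The plan should be changed, but its powered outcomes still stand.

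**What to change.** 1. **Recurrence.** Add one yes/no REDCap item, worded identically in both arms, at each of the six postoperative contacts: has the operated finger caught or locked, or been treated again, since the last contact (since surgery, at the first one)? Write one definition of recurrence and one of incomplete release. The item alone cannot separate the two, so ascertain both in the same way in both arms from the item plus visit and chart data. Report the number answering per arm at each contact.
2. **Six-month measurements.** Make no formal between-arm test of motion, crease distance or grip at 6 months. Report the values descriptively, labeled as coming from patients seen for persistent problems. Make month 3 the last formal test. Report the number measured per arm at every visit and read the month-3 result against those counts, because that contact may also be by telephone.
3. **Grip.** Reconcile the two passages to one setting for every visit and both arms, and record the setting used.

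**Cost.** Protocol wording, one REDCap item and a table of counts, with no added visits. Patients answer one more question at six contacts, staff check charts for positive answers, and the study gives up a formal 6-month test of three secondary endpoints.
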